### 11.2 Primary and Co-primary Efficacy Endpoints

The primary endpoint time is

- D-dimer at day 7 post randomization

The co-primary endpoint is the following:

- Seven-category ordinal scale recommended by the WHO at day 7 post randomization (Attachment 2)

The primary efficacy endpoint is D-dimer at day 7 post randomization will adjusted for baseline measurement. The logarithmic D-dimer measurements (using the natural logarithm) will be analyzed by an analysis of covariance (ANCOVA). The model will include treatment group and stratification variables of the randomization as factors and the logarithmic baseline D-dimer measurement as covariate. Least squares means for D-dimer at day 7 in the two treatment groups will be presented with 95% confidence intervals as well as the difference between the treatment groups at day 7 with 95% confidence interval and p-value testing the null hypothesis of no treatment difference, i.e. a mean difference (on the

logarithmic scale) of 0. For ease of interpretation the results will also be converted to the original measurement scale.

The co-primary endpoint is the seven-category ordinal scale recommended by the WHO (Attachment 2) at day 7 post randomization adjusted for baseline score. Frequencies and percentages of the scores at day 7 will be provided stratified by treatment group. The distributions of the scores will be compared between the two treatment groups using a nonparametric Wilcoxon (Mann-Whitney) rank-sum test stratified by baseline score dichotomized as smaller or equal 3 vs. larger 3. The treatment effect will be reported as probabilistic index or relative effect, i.e. the probability that an observation in the treatment group will be smaller (more favourable) than an observation in the control group, with 95% confidence interval.

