## 5. TREATMENT ALLOCATION AND BLINDING

### Treatment Allocation

#### Procedures for Randomization and Stratification

This trial is an open label study. Central randomization will be implemented in this study. Subjects will be randomly assigned to 1 of 2 treatment groups (rivaroxaban or SOC with prophylactic UFH or LMWH) in a 1:1 fashion based on a computer-generated randomization schedule prepared before the study starts under the supervision of the sponsor. Randomization will follow a dynamic randomization algorithm with residual randomness designed to minimize imbalance in terms of variance between treatments taking the following stratification factors into account: site, gender (male, female, diverse), age (< 65 versus  $\geq$  65 years), kidney function (eGFR  $\geq$  30 mL/min/1.73m^2 and < 50 mL/min/1.73m^2 versus eGFR  $\geq$  50 mL/min/1.73m^2), history of CAD or heart failure (yes/no), oxygen demand on admission to the hospital (supplementary oxygen required versus not required) and setting (outpatients versus hospitalized patients). The computer system will dictate the treatment assignment for the subject. The requestor must use his or her own user identification and personal identification number when contacting the system and will then give the relevant subject details to uniquely identify the subject.

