Longitudinal ordinal data (a seven-category ordinal scale) assessed at day 7, 35 and 60 will be analyzed using a proportional odds model with treatment, visit, treatment-by-visit interaction, baseline score and stratification variables of the randomization as factors. The correlation in longitudinal assessments within the same patient will be accounted for by random patient effects. Binary data (e.g. development of DIC) will use similar generalized linear mixed effect models but with logit link function.

All stratification variables of the randomization (site, gender (male, female, diverse), age (< 65 versus  $\geq$  65 years), kidney function (eGFR  $\geq$  30 mL/min/1.73m^2 and < 50 mL/min/1.73m^2 versus eGFR  $\geq$  50 mL/min/1.73m^2), history of CAD or heart failure (yes/no), oxygen demand on admission to the hospital (supplementary oxygen required versus not required), setting (outpatients versus hospitalized patients)) will be included as factors in the analyses of the secondary endpoints.

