## 11.7 Sample size determination

Sample size calculation is based on the primary endpoint D-dimer at day 7 corrected for baseline values. Since the distribution of D-dimer concentrations is skewed, calculations are done on the log scale. Using an analysis of covariance (ANCOVA) (significance level  $\alpha=0.05$  two-sided) with baseline values as covariate a total sample size of 80, i.e. 40 per group, gives a power of 80% to detect a mean difference of 0.44 (on the log scale) between the treatment group and the control group at day 7. Based on a blinded review, a common standard deviation of SD=0.8 and a correlation to baseline of  $r=0.5$  (both on the natural log scale) were assumed. The effect assumed translates to a reduction of 36% in D-Dimer values on the original scale. The co-primary endpoint is a seven-category ordinal scale previously recommended by the WHO (Attachment 2) as clinical improvement scale for patients with respiratory infections. Here 40 patients per group will give a power of 80% to detect a relative treatment effect  $p_1=0.68$  between treatment and control group at day 7 using a Wilcoxon (Mann-Whitney) rank-sum test (two sided,  $\alpha=0.05$ ). The probabilistic index or relative effect  $p_1$  denotes the probability that an observation in the treatment group will be less than an observation in the control group. Targeting a total of at least 80 evaluable patients, we aim to recruit about 100 patients.

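### The co-primary day-7 ordinal test adjusts only for a two-level baseline score; if the omitted allocation factors are prognostic, it is conservative and its confidence interval too wide

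*Protocol*

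**What the plan says.** Protocol section 5 describes the allocation: "Randomization will follow a dynamic randomization algorithm with residual randomness designed to minimize imbalance in terms of variance between treatments". The factors are site, gender, age group, kidney function, history of CAD or heart failure, oxygen demand on admission, and setting (outpatient or hospitalised). The ratio is 1:1.

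Section 11.2, repeated in the Synopsis, puts these factors in the ANCOVA for D-dimer. Section 11.3 puts them in the Cox models, in the MMRM, and in the longitudinal analysis of the same seven-category scale, a "proportional odds model with treatment, visit, treatment-by-visit interaction, baseline score and stratification variables of the randomization as factors".

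The co-primary comparison in section 11.2 is the exception. It is a "nonparametric Wilcoxon (Mann-Whitney) rank-sum test stratified by baseline score dichotomized as smaller or equal 3 vs. larger 3". The endpoint is described there as adjusted for baseline score, and a relative effect with a 95% confidence interval is promised. No reason is given for treating this endpoint differently.

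Section 11.7 gives the power statement: "Here 40 patients per group will give a power of 80% to detect a relative treatment effect" of 0.68, with a "Wilcoxon (Mann-Whitney) rank-sum test (two sided", 5% level). On numbers it says: "Targeting a total of at least 80 evaluable patients, we aim to recruit about 100 patients".

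**The concern.** When allocation forces balance on a factor that predicts the outcome, the chance imbalance in that factor is largely removed from the treatment contrast. A test that ignores the factor still counts that variation in its null variance. Its standard error is then too large, its p-value too large and its interval too wide. The error is on the conservative side; type I error is not inflated.

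The single stratifier covers this only in part. In Attachment 2, category 3 is a ward patient without oxygen and category 4 a ward patient on oxygen, so the cut lies close to oxygen demand. It also carries some information on setting, because outpatients should fall at or below 3. Within that lower stratum, however, outpatients (who would naturally score 1 or 2) are pooled with inpatients not on oxygen (score 3). The outpatient starts in a range that the inpatient reaches only by discharge. Since hospital status is part of the outcome scale, setting is likely to be prognostic inside that stratum. Age and history of CAD or heart failure are not represented at all.

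At stake is the precision of the only clinical measure among the two primary comparisons. The amendment rationale in section 18.1 says that no further patients are to be recruited, so precision can now come only from the analysis.

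**Working it through.** **1. The plan's own figure.** Inputs from section 11.7: p1 = 0.68, 40 per group (N = 80), two-sided 5%, 80% power. Noether's formula for the rank-sum test:

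- N = (1.960 + 0.842)² / (3 × 0.18²) = 80.7.
- Power at N = 80: Φ(0.18 × √240 − 1.960) = Φ(2.789 − 1.960) = Φ(0.829) = 79.6%.

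The stated 80% reproduces for a test without covariate adjustment.

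**2. Effect of omitting balanced factors, by formula.** Let R² be the share of rank variance that the omitted factors explain beyond the two-level baseline score. The protocol gives no value, so a range is shown. If allocation balances the factors fully:

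- Actual level of the planned test: 2Φ(−1.960/√(1−R²)).
- Power of the planned test: Φ(0.829/√(1−R²)), because its true variance also shrinks.
- Power of an adjusted test: Φ(2.789/√(1−R²) − 1.960).

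| R² | Actual level | Planned power | Adjusted power | Gain (points) |
|---|---|---|---|---|
| 0.05 | 4.4% | 80.2% | 81.6% | 1.4 |
| 0.12 | 3.7% | 81.1% | 84.4% | 3.3 |
| 0.15 | 3.4% | 81.6% | 85.6% | 4.1 |
| 0.19 | 2.9% | 82.1% | 87.3% | 5.1 |
| 0.20 | 2.8% | 82.3% | 87.7% | 5.4 |
| 0.25 | 2.4% | 83.1% | 89.6% | 6.6 |

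A gain of 5 points needs R² near 0.19. Full balance is a limit; real minimisation with a random element gives somewhat smaller effects at low and moderate R².

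**3. Simulation.** Two sets of simulated trials used minimisation on all seven factors and the planned two-stratum test. Factor prevalences, number of sites, biased-coin probability and prognostic strength are assumptions, not protocol values.

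*Set A*: N = 80, 8 sites, coin 0.80, 20% outpatients. The comparator is a rank ANCOVA adjusted for oxygen/baseline score, setting, age and CAD or heart failure.

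| Omitted factors | Level, planned | Level, adjusted | Power, planned → adjusted |
|---|---|---|---|
| Weak (R² about 0.07) | 4.4% | 5.1% | no difference |
| Moderate (about 0.14) | 3.9% | 5.1% | 62.8→65.8, 73.9→76.0, 84.7→86.8% |
| Strong (about 0.24) | 3.1% | 5.1% | 55.9→65.1, 68.2→74.8, 80.8→85.6% |

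*Set B*: N = 80 and 100, 5 and 14 sites, coin 0.80 and 0.95. The comparator is a rank ANCOVA on baseline stratum plus all seven factors.

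| Omitted factors | Level, planned | SE overstated | Power change, all seven adjusted |
|---|---|---|---|
| Not prognostic | 4.6–5.4% | about 0% | −8 to −1 points |
| Moderate | 3.8–4.7% | 4–6% | −3 to +2 points |
| Strong | 2.3–2.8% | 12–16% | +10 to +15 points |

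With site left out, the moderate case in Set B gains 0.5 to 2 points. The losses come mainly from spending many site terms on 80 to 100 patients.

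**4. Does the stated power fail?** In Set B with the overall effect at p1 = 0.68, 40 per arm and coin 0.80, the planned test has simulated power of 0.89 to 0.97. The stated 80% is not undercut.

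**5. Which strength is plausible?** With assumed day-7 distributions and 5 to 30% outpatients, setting alone explains 4 to 15% of rank variance in the lower stratum and about 3 to 10% overall. That points to the weak-to-moderate range before age and CAD or heart failure are added.

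**The case against.** The strongest reply is that this is an efficiency preference in a study that section 11 declares exploratory. No stated figure fails, the error is on the safe side, and the proportional odds model in section 11.3 already yields an adjusted day-7 effect on the same scale. Exclusion criterion 4 removes patients about to enter ICU, so baseline categories 5 and 6 should be rare and the upper stratum is nearly category 4 alone; the dichotomy loses little there. Much of this stands and limits the size of the point. It does not explain why the co-primary analysis alone omits the allocation factors. The longitudinal model is a secondary analysis, so the co-primary p-value and interval still come from the stratified test.

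Three stronger readings are tempting and are not supported.

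- **That the test runs below 5% and loses power as a matter of course.** Both depend on prognostic strength, which the documents do not give. If the factors add nothing beyond the baseline stratum, the level is about 5% and adjustment gains nothing. Power is lost only relative to an adjusted analysis.
- **That a 5-point gain already appears at R² of 0.12 to 0.13.** This follows from comparing adjusted power with 79.6%. That figure ignores minimisation, which also reduces the true variance of the planned test. On the proper comparison the gain at 0.12 is 3.3 points.
- **That the test covers oxygen demand and omits the other six factors.** Baseline score is not an allocation factor: oxygen demand is taken on admission, the score at randomisation (section 9.1.3). Strictly none of the seven is in the test, though the cut partly reflects two of them.

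**Conclusion.** The point holds in conditional form. The co-primary test leaves out all seven allocation factors as such, unlike the other main efficacy models, and gives no reason. If those factors are prognostic beyond the baseline dichotomy, the test is conservative and its interval too wide.

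Under assumed moderate strength the actual level is about 4 to 4.7%, the standard error is 4 to 6% too large, and a sparing adjustment gains about 0 to 3 points of power. Under assumed strong prognosis the figures are about 2 to 3%, 12 to 16%, and 5 points or more. The scale and the pooling of outpatients with inpatients make some residual effect of setting likely, more probably weak to moderate than strong. The change is worth making because it is cheap and the sample cannot grow; the planned test is valid as it stands.

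**What to change.** In section 11.2 and the Synopsis, make the co-primary analysis of the day-7 score a rank ANCOVA (extended Wilcoxon) with treatment, baseline score, setting, age group (<65, ≥65) and history of CAD or heart failure. Leave site out as a fixed factor and merge empty or sparse levels. Report the adjusted relative effect with its 95% confidence interval: 0.5 plus the adjusted difference in mean ranks (control minus rivaroxaban) divided by N, with ties counted as a half. Keep the planned stratified Wilcoxon test as a sensitivity analysis. Fix this in writing before any treatment-group data are analysed; with an open-label design and 111 patients already randomised, the timing should be documented.

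The cost is wording, a few lines of code and three or four extra parameters; the covariates are already collected. If the factors prove not to be prognostic there is no gain, and under 1 point of power was lost in simulation with this short covariate list. Adjusting for all seven factors including site could cost more, up to 8 points in that case, and is not advised.

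### The co-primary effect is defined as the probability of a strictly smaller score, with no weight for ties, so its no-effect value on the seven-category scale cannot be the 0.5 that the test and sample size presuppose

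*Protocol*

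**What the plan says.** The co-primary endpoint is the seven-category ordinal score at day 7 (Protocol, Attachment 2), on which lower scores are better. Section 11.2 compares the arms with a Wilcoxon "rank-sum test stratified by baseline score dichotomized as smaller or equal 3 vs. larger 3". On the effect measure it says: "The treatment effect will be reported as probabilistic index or relative effect, i.e." The definition then follows: "the probability that an observation in the treatment group will be smaller (more favourable) than an observation in the control group", to be given with a 95% confidence interval.

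Section 11.7 says: "Here 40 patients per group will give a power of 80% to detect a relative treatment effect" of p1=0.68, "using a Wilcoxon (Mann-Whitney) rank-sum test (two sided", alpha 0.05). It adds that p1 "denotes the probability that an observation in the treatment group will be less than an observation in the control group".

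The Synopsis carries the same two definitions, one in its statistical methods and one in the sample-size paragraph of its design overview. None of the four places mentions ties or states the value of the index under no effect.

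**The concern.** The rank-sum test addresses P(T<C) + 0.5 P(T=C), where T and C are the scores of a random treated and a random control patient. This quantity is 0.5 when the arms have the same distribution, whatever the number of ties. The protocol's wording keeps only the first term. For a continuous outcome the two agree. On seven categories they do not, because many treated-control pairs share a score.

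A programmer who follows the wording would produce an index whose no-effect value lies below 0.5 and depends on the unknown score distribution. Readers would still judge it against 0.5, the usual reference for a measure with this name and the one implied by the sample size. At stake are the point estimate and confidence interval of a co-primary endpoint. In a study that calls itself explorative, these carry much of the interpretation.

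**Working it through.** **Inputs from the protocol:** p1 = 0.68, 40 per group, power 80%, two-sided alpha 0.05 (section 11.7); 1:1 allocation (section 5); seven categories (Attachment 2). **Assumed:** the day-7 score distributions, and a common (proportional) odds ratio as the form of benefit.

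**1. The plan's own figure.** Noether's formula with null value 0.5:

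N = (1.960 + 0.842)² / (12 × 0.25 × (0.68 − 0.5)²) = 7.849 / (3 × 0.0324) = 80.7 in total.

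Power at N = 80 is 79.6%. The stated 80 patients and 80% power reproduce, with the no-effect value set at 0.5.

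**2. No-effect value as written.** With identical category probabilities p_k in both arms, P(T<C) = P(T>C), so

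P(T<C) = (1 − P(tie))/2, with P(tie) = Σ p_k².

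On seven categories Σ p_k² is smallest when all are equal, at 1/7. So P(T<C) ≤ (1 − 1/7)/2 = 3/7 = 0.429. This bound needs no assumption about the distribution. With ties counted as one half the value is always 0.500.

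**3. One assumed distribution**, categories 1 to 7: 0.15, 0.35, 0.15, 0.25, 0.03, 0.05, 0.02.

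- P(tie) = 0.0225 + 0.1225 + 0.0225 + 0.0625 + 0.0009 + 0.0025 + 0.0004 = 0.234.
- No effect as written: (1 − 0.234)/2 = 0.383.
- Odds ratio 1.8 in favour of rivaroxaban: treated probabilities become 0.241, 0.402, 0.127, 0.172, 0.018, 0.029, 0.011. P(T<C) = 0.241×0.85 + 0.402×0.50 + 0.127×0.35 + 0.172×0.10 + 0.018×0.07 + 0.029×0.02 = 0.469. P(tie) = 0.241. With half-ties: 0.469 + 0.121 = 0.590.
- Odds ratio 3.3: 0.557 as written, 0.675 with half-ties. Odds ratio 3.5: 0.565 and 0.683. The planned 0.68 lies between these and would read about 0.56.

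**4. Range over other assumed distributions.**

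| Assumed control distribution | No effect, as written | Odds ratio 2, as written | Odds ratio 2, half-ties |
|---|---|---|---|
| Uniform over seven categories | 0.429 | 0.540 | 0.611 |
| Spread over seven categories | 0.402–0.403 | 0.509–0.514 | 0.608–0.609 |
| Hospital-type mixes | 0.377–0.388 | 0.474–0.500 | 0.603–0.607 |
| 45% in one category | 0.356 | 0.446 | 0.599 |
| Three equal categories | 0.333 | 0.433 | 0.600 |
| 60% in one category | 0.294 | 0.345 | 0.580 |

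Across all of them a half-tie effect of 0.68 would read 0.44 to 0.61.

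**5. Behaviour in repeated trials** (simulated, 40 per group, unstratified, the distribution of step 3). Under no effect, the 95% interval for the index as written lies wholly below 0.5 in about 45% of trials. At odds ratio 1.8, about 67% of point estimates fall below 0.5. In about 30% of all trials the test is significant for rivaroxaban while the interval does not lie above 0.5.

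**6. The test itself.** At a half-tie index of 0.68, simulated power of the unstratified, tie-corrected rank-sum test with 40 per group is 84% to 87% in three of the assumed distributions. Ties do not weaken the sample-size statement.

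**The case against.** The strongest reply is that the sponsor plainly means the half-tie version. The measure carries the standard name, is paired with the Wilcoxon test, and has a planning value that reproduces with a null of 0.5. The verbal definition may be loose shorthand, and the SAP, which is not shown, may give the tie handling. Scores are also tabulated by arm, so the direction of effect would remain visible. This stands as to intent and limits the practical risk. It does not remove the error: the protocol states a definition, in four places, that disagrees with its own sample size.

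A reader might infer more than the documents support:

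- **That an interval wholly below 0.5 would accompany a significant benefit.** In simulations over five assumed distributions (tie probability 0.19 to 0.28) and odds ratios 1.5 to 3.5, this occurred in 0 of 4,000 runs in every scenario. It appeared, in 1% to 6% of runs, only with 60% of controls in one category.
- **That the no-effect value is a known figure such as 0.35 to 0.39.** That needs a tie probability of about 0.22 to 0.30, which the protocol does not give. Only the bound of 0.429 is free of assumptions.
- **That the index ignores the stratification, or that the strata should be redrawn by setting.** Section 11.2 does not say how the index is pooled across strata, and that is ordinary SAP detail. Splitting the lower stratum would add only 1 to 3 points of power on assumed data. It would also presume that outpatients sit in categories that Attachment 2 reserves for discharged patients.

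**Conclusion.** The definition is wrong as written. Without a term for ties, the co-primary effect measure has a no-effect value of at most 0.429 on this scale (about 0.29 to 0.43 over the distributions tried), whereas the test and the 40 per group rest on 0.5. Applied literally, the estimate and interval could suggest harm when there is none, or hide a modest benefit.

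The bound of 0.429 and the mismatch with section 11.7 follow from the protocol alone. Every other figure depends on assumed day-7 distributions and proportional odds. The p-value and the sample size are unaffected. The point concerns only how the effect is defined and reported.

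**What to change.** In sections 11.2 and 11.7, and in the two matching Synopsis paragraphs, define the relative effect as the probability that a treated patient's score is smaller than a control patient's, plus one half of the probability that the two are equal: P(T<C) + 0.5 P(T=C). State that the value under no effect is 0.5, that values above 0.5 favour rivaroxaban, and that the estimate and its 95% confidence interval are reported on this scale. The planning value p1=0.68 can stay as it is.

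The cost is about one sentence in each of the four places and trivial programming. Test, strata and sample size do not change.

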### 11.3 Secondary Efficacy Endpoint

The secondary combined endpoint includes

Time to first event of either

- Venous thromboembolism (VTE) (deep venous thrombosis (DVT) and/or fatal or non-fatal pulmonary embolism (PE))
- Arterial thromboembolism
- New myocardial infarction (MI)
- Non-hemorrhagic stroke
- All-cause death
- Progression to intubation and invasive ventilation

Time to first event of either of the components of the secondary composite endpoint will be analyzed using a Cox proportional hazards regression model with treatment and the stratification variables of the randomization (site, gender (male, female, diverse), age (< 65 versus  $\geq$  65 years), kidney function (eGFR  $\geq$  30 mL/min/1.73m^2 and < 50 mL/min/1.73m^2 versus eGFR  $\geq$  50 mL/min/1.73m^2), history of CAD or heart failure (yes/no), oxygen demand on admission to the hospital (supplementary oxygen required versus not required), setting (outpatients versus hospitalized patients)) as factors. The treatment effect will be reported as hazard ratio (HR) with 95% confidence interval and p-value for the null hypothesis H0: HR=1. The primary endpoint will be visualized as Kaplan-Meier curves. Sensitivity analyses will explore the robustness of these analyses.

The analyses of the time-to-event outcomes among the secondary endpoints (such as time to VTE, time to arterial thromboembolism, time to new MI, time to non-hemorrhagic stroke, time to all-cause death, time to progression to intubation and invasive ventilation) will follow the same lines as the analysis of the composite outcome, i.e. survival analyses comprising Cox proportional hazard regression models and Kaplan-Meier curves. Death will be treated as a competing event except when analyzing all-cause death, naturally.

Longitudinal D-dimer measurements assessed at day 7, 35 and 60 will be analyzed on the logarithmic scale using a mixed model for repeated measures (MMRM) approach. The model will include treatment, visit, treatment-by-visit interaction and stratification variables of the randomization as factors as well as logarithmic D-dimer baseline value as covariate. The residuals will be assumed to follow a multivariate normal distribution with unstructured covariance matrix. LS means of the group means and their differences will be computed for the various timepoints and reported with 95% confidence intervals.

Longitudinal ordinal data (a seven-category ordinal scale) assessed at day 7, 35 and 60 will be analyzed using a proportional odds model with treatment, visit, treatment-by-visit interaction, baseline score and stratification variables of the randomization as factors. The correlation in longitudinal assessments within the same patient will be accounted for by random patient effects. Binary data (e.g. development of DIC) will use similar generalized linear mixed effect models but with logit link function.

All stratification variables of the randomization (site, gender (male, female, diverse), age (< 65 versus  $\geq$  65 years), kidney function (eGFR  $\geq$  30 mL/min/1.73m^2 and < 50 mL/min/1.73m^2 versus eGFR  $\geq$  50 mL/min/1.73m^2), history of CAD or heart failure (yes/no), oxygen demand on admission to the hospital (supplementary oxygen required versus not required), setting (outpatients versus hospitalized patients)) will be included as factors in the analyses of the secondary endpoints.

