## Secondary Efficacy Endpoints

Secondary composite endpoint includes

Time to first event of either of

- Venous thromboembolism (VTE) (deep venous thrombosis (DVT) and/or fatal or non-fatal pulmonary embolism (PE))
- Arterial thromboembolism
- New myocardial infarction (MI)
- Non-hemorrhagic stroke
- All-cause death
- Progression to intubation and invasive ventilation

as well as each component of the secondary composite endpoint as described above, if sufficient numbers of events will be observed.

Time to first event of either of the components of the secondary composite endpoint will be analyzed using a Cox proportional hazards regression model with treatment and the stratification variables of the randomization (site, gender (male, female, diverse), age (< 65 versus  $\geq$  65 years), kidney function (eGFR  $\geq$  30 mL/min/1.73m^2 and < 50 mL/min/1.73m^2 versus eGFR  $\geq$  50 mL/min/1.73m^2), history of CAD or heart failure (yes/no), oxygen demand on admission to the hospital (supplementary oxygen required versus not required), setting (outpatients versus hospitalized patients)) as factors. The treatment effect will be reported as hazard ratio (HR) with 95% confidence interval and p-value for the null hypothesis H0: HR=1. The primary endpoint will be visualized as Kaplan-Meier curves. Sensitivity analyses will explore the robustness of these analyses.

The analyses of the time-to-event outcomes among the secondary endpoints (such as time to VTE, time to arterial thromboembolism, time to new MI, time to non-hemorrhagic stroke, time to all-cause death, time to progression to intubation and invasive ventilation will follow the same lines as the analysis of the composite endpoint, i.e. survival analyses comprising Cox proportional hazard regression models and Kaplan-Meier curves. Death will be treated as a competing event except when analyzing all-cause death, naturally.

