### 11.1 Definition of populations included in the analyses

The primary efficacy analysis as well as all secondary efficacy analyses will be based on the full analysis set (FAS) following the intention-to-treat principle and will include all randomized patients. Safety analyses will be based on the safety set (SAF) including all randomized patients with at least one dose of study medication or at least one dose of SOC (UFH or LMWH).

For time-to-event endpoints, study discontinuations will be dealt with as independent right censoring. Patients discontinuing study drug will be follow up for endpoints. Otherwise missing values will be dealt with using multiple imputation methods. If, against expectations, the proportion of patients with premature study discontinuations is substantial, shared random effects models simultaneously modelling time to primary outcome and time to study discontinuation will be used to explore the robustness of the treatment effect.

Sensitivity analyses will be performed in all patients (a) completing at least 7 days of treatment and (b) completing the study adherent to the study protocol. These will be referred to as the (a) while on treatment population and (b) per-protocol (PP) population.

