## 11.5 Safety Endpoints

Safety analyses will follow standard procedures for the reporting of adverse events; these will be reported as frequencies (percentages) by treatment group. All safety analyses will be based on the safety set. One safety endpoint of particular interest are bleeding events (see Section 9.3.1). The time to bleeding events will be analyzed in a Cox proportional hazards model, if a sufficient number of events will be observed. Treatment group differences will be reported as hazard ratios with 95% confidence intervals and p-values testing the null hypothesis of no group difference (i.e. HR=1). The estimation of the probability for bleeding events will account for competing events such as death and premature study discontinuation using the Aalen-Johansen estimator, the so-called cumulative incidence function.

Differences between treatment groups in continuous laboratory parameters and vital signs over follow-up time will be explored in longitudinal box plots.

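### Kaplan-Meier curves are prescribed for the non-fatal components although death is declared a competing event; 1 minus Kaplan-Meier then modestly overstates their incidence

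*Protocol*

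**What the plan says.** Section 11.3 of the protocol lists the single time-to-event outcomes ("such as time to VTE, time to arterial thromboembolism, time to new MI, time to non-hemorrhagic stroke, time to all-cause death", and progression to intubation and invasive ventilation). It says that they are analysed like the composite, by "survival analyses comprising Cox proportional hazard regression models and Kaplan-Meier curves. Death will be treated as a competing event", the analysis of all-cause death itself being the one exception. The Synopsis has the same pair of sentences; there the components "will follow the same lines as the analysis of the composite endpoint, i.e. survival analyses comprising Cox proportional hazard regression models and Kaplan-Meier curves".

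For bleeding, Section 11.5 handles the same difficulty differently: the probability estimate "will account for competing events such as death and premature study discontinuation using the Aalen-Johansen estimator, the so-called cumulative incidence function".

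Section 11.1 sets the censoring rule: "For time-to-event endpoints, study discontinuations will be dealt with as independent right censoring". It does not mention death. Section 2.1 makes the component analyses conditional on enough events, and Section 11 calls the whole study explorative.

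**The concern.** A Kaplan-Meier curve for a single non-fatal event, drawn in the usual way, removes patients from the risk set at death as if they could still have had the event later. Its complement describes a setting without death, not the proportion of trial patients who have a VTE, an MI, a stroke or an intubation. Treating death as a competing event means the opposite: patients who have died can no longer contribute an event. The curve named in one sentence therefore does not deliver the role given to death in the next, and an analyst has to choose which sentence to follow.

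At stake are the component incidences read off the curves at day 35. They come out too high. When event hazards and the timing of deaths are similar in the two arms, the arm with more deaths is overstated more.

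**Working it through.** The plan states no figure on this point, so there is nothing of its own to reproduce. The size is worked out under stated assumptions.

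**Inputs.** The horizon is day 35 (Section 2.2). Component incidence and mortality are assumed, because the protocol gives neither for its population. Hazards are taken as constant.

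**Formulas.** Let *p* be the true cumulative incidence of the component by day 35 and *d* the proportion who die first.

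- Total cumulative hazard: H = −ln(1 − p − d)
- Cumulative hazard of the component: L = H × p/(p + d)
- What the curve shows: 1 − KM = 1 − exp(−L)

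**Results for p = 10%.**

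| Deaths first, d | H | L | 1 − KM | Excess (points) | Relative excess |
|---|---|---|---|---|---|
| 5% | 0.1625 | 0.1083 | 10.27% | 0.27 | 2.7% |
| 15% | 0.2877 | 0.1151 | 10.87% | 0.87 | 8.7% |
| 20% | 0.3567 | 0.1189 | 11.21% | 1.21 | 12.1% |
| 30% | 0.5108 | 0.1277 | 11.99% | 1.99 | 19.9% |

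For example, at d = 20%: H = −ln(0.70) = 0.3567; L = 0.3567 × 0.10/0.30 = 0.1189; 1 − exp(−0.1189) = 0.1121.

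**Check from the other side.** Fix 1 − KM at 10% and let *D* be the death risk in the absence of the event. With L = −ln(0.90) and M = −ln(1 − D), the Aalen-Johansen value is L/(L + M) × (1 − exp(−(L + M))).

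- D = 5%, 10% and 20% give 9.75%, 9.50% and 8.98%, so the excess is 0.25, 0.50 and 1.02 points.
- The same event hazard in both arms with D = 5% against 15% gives an excess of 0.25 against 0.76 points.

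**Simulation.** In 5,000 simulated arms of 50 patients at 10% event risk and 10% death risk, 1 − KM was never below the Aalen-Johansen estimate. The mean excess was 0.50 points, as the formula predicts.

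**Sensitivity.**

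- If the 10% death risk falls entirely in the last week before day 35, the excess shrinks to about 0.1 point.
- An arm with a much higher event rate can have the larger absolute excess despite fewer deaths: 1 − KM of 31% with 5% deaths gives 0.7 points, and 5% with 10% deaths gives 0.25 points. The ordering by mortality is therefore a statement about the relative excess.

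**Against sampling error.** With about 100 patients (Section 11.7), an arm has about 50. The standard error of a 10% proportion is √(0.10 × 0.90/50) = 4.2 points.

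**The case against.** The strongest defence is that the competing-event sentence follows directly on the Kaplan-Meier sentence and can be read as qualifying it, with the estimator left to the analysis plan that Section 11 announces. This would succeed if the protocol were silent on the curve. It is not silent: it names Kaplan-Meier in two places, and Section 11.5 shows that the authors name another estimator when they intend one.

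The other objections limit the size of the point, and they stand:

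- The effect measure is the Cox hazard ratio. A Cox model that censors at death is a valid cause-specific analysis. Only the curves and the probabilities read from them are at fault.
- The composite contains all-cause death, so Kaplan-Meier is right for it and for all-cause death alone.
- Fatal PE counts as a VTE event, so only other deaths compete with VTE.
- Outpatients are eligible, and patients too critically ill to consent are excluded. The high mortality figures in the background section therefore cannot be carried over to this trial.

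Four stronger readings are tempting but not supported.

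1. *A Kaplan-Meier curve can only censor deaths.* If patients who die are kept in the risk set to day 35 and there is no other censoring, 1 − KM equals the cumulative incidence. The protocol does not say that deaths are censored; the overstatement belongs to the usual practice.
2. *Benefit and risk would be on different scales.* Section 9.4 says only that benefit-risk will be explored and plans no comparison of component curves with bleeding curves.
3. *The curves would create a treatment difference out of nothing.* With 10% true incidence in both arms and deaths of 5% against 20%, the curves show 10.3% against 11.2%. But the cause-specific hazards then truly differ (0.1189/0.1083 = 1.10), and a cause-specific hazard ratio would point the same way.
4. *Section 11.5 can be copied as it stands.* It also treats premature study discontinuation as a competing event, whereas Section 11.1 censors it.

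**Conclusion.** The point holds as a modest one. Section 11.3 and the Synopsis name a curve that conflicts with the role they give to death, for five components. With deaths censored in the usual way, component incidence is overstated by about 0.3 points at 5% deaths and 1.2 points at 20% deaths, for a true incidence of 10% under constant hazards. These rates are assumptions, and the excess is smaller if deaths come late. It is well below the sampling error of an arm of about 50. It is nevertheless systematic and upward, and relatively larger where more patients die at similar times.

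Nothing confirmatory depends on it. The primary and co-primary analyses, the composite, all-cause death and the hazard ratios are untouched, and the component analyses are exploratory and conditional on enough events. The reason to correct it is that the two instructions conflict and the right method costs almost nothing.

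**What to change.** In Section 11.3 and in the Synopsis:

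- Keep Kaplan-Meier curves for the composite and for all-cause death.
- For every other component, present Aalen-Johansen cumulative incidence curves by arm with death as the competing event. Deaths that are themselves the component event, such as fatal PE for VTE, count as events.
- State that study discontinuation is censored in these curves, as in Section 11.1.
- Label the Cox hazard ratios for these components as cause-specific.

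The cost is a sentence or two in each place. It needs no new data and only standard software.
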